**Table 1: PTX-35 Dose Levels**

Dose level*	PTX-35 dose (mg/kg)	PTX-35 Concentration (mg/mL)	PTX-35 Dose (mL/kg)	Number of patients
1	0.01 mg/kg	1 mg/mL	0.01 mL/kg	3-6
2	0.03 mg/kg	1 mg/mL	0.03 mL/kg	3-6
3	0.10 mg/kg	1 mg/mL	0.10 mL/kg	3-6
4	0.30 mg/kg	5 mg/mL	0.06 mL/kg	3-6
5	1.0 mg/kg	5 mg/mL	0.20 mL/kg	3-6
6	3.0 mg/kg	5 mg/mL	0.60 mL/kg	3-6
7	10 mg/kg	5 mg/mL	2.0 mL/kg	3-6

*\*Dose levels 1 through 3 will be administered at a concentration of 1 mg/mL, and dose levels 4 through 7 will be administered at a concentration of 5 mg/mL.*

At each dose level, 3 patients will be enrolled, with a minimum waiting period of one week after treatment initiation of the first patient only. The remaining subjects in the dose level will be treated with no stagger. After all 3 patients in a dose level have received the second dose of PTX-35 and completed the DLT observation period, the Safety Review Committee (SRC) will review the safety data to make a dose escalation decision. If none of these 3 patients experiences a DLT, dose escalation may proceed. If 1 of these 3 patients experiences a DLT, the dose level will be expanded to at least 6 patients at the same dose level. If  $\leq 1$  out of 6 patients experiences a DLT, then the SRC may recommend dose escalation to the next dose level. If a DLT occurs in 2 or more patients in a particular dose level, the maximum tolerated dose (MTD) has been exceeded and dose escalation will cease. Up to 3 additional patients will be enrolled at the next lowest dose if only 3 patients were treated at that dose level, to confirm safety of that dose.

The conduct and completion of each subsequent dose cohort will follow in similar fashion until the MTD is established. Note that if the optimal immunological dose (OID), or observed plateau of Treg activity, is determined prior to MTD, further dose escalation may be discontinued by decision of the SRC.

Visits and study examinations will be performed per [Table 2: Schedule of Assessments](#). Safety will be assessed by frequency of treatment-emergent adverse events (TEAEs), evaluation of clinical laboratory parameters (hematology and biochemistry), weight, vital signs, electrocardiogram (ECG), performance status, and physical exam findings. NCI CTCAE version 5.0 will be used to grade all toxicities.

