### 6.1.3 Dose-Limiting Toxicity

An event will be considered a DLT per NCI CTCAE version 5.0 criteria if it occurs within the DLT reporting period during Cycle 1 and Cycle 2 (i.e., 4 week evaluation period following the initial administration of PTX-35) and meets at least one of the criteria below:

- Hematological toxicities  $\geq$  Grade 3
- Non-hematological toxicities  $\geq$  Grade 3
- Cytokine release syndrome  $\geq$  Grade 3
- Infusion reaction  $\geq$  Grade 3
- Any  $\geq$  Grade 3 hepatic toxicity meeting Hy's Law criteria, or total bilirubin  $\geq 2.0 \times$  ULN to  $\leq 3.0 \times$  ULN for  $>7$  consecutive days,  $\geq$  CTCAE G3 total bilirubin, CTCAE G3 AST or ALT for  $>7$  consecutive days, or CTCAE G4 AST or ALT
- Any other treatment-emergent toxicity that is considered clinically significant and/or unacceptable, and that does not respond to supportive care and results in a disruption of the treatment schedule of more than 14 days.

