#### DLT excludes:

- Hematological and non-hematological  $\leq$  Grade 2 unless considered non-acceptable.
- Other Grade 3 self-limited or medically controllable toxicities (e.g., fever without  $\geq$  Grade 3 neutropenia, lymphopenia, nausea, vomiting, diarrhea, fatigue). Note, such events are considered DLT if the abnormality leads to hospitalization or the abnormality persists for  $>72$  hours despite appropriate interventions (e.g., replacement therapy for electrolyte abnormalities, when indicated).
- Electrolyte disturbances that are managed to Grade 1 or less with supplemental therapy.

Any adverse event that is potentially related to PTX-35 and requires discontinuation of treatment should be considered a DLT. A DLT will be considered related to PTX-35 treatment unless there is a clear, well-documented relation to intercurrent illness or primary malignant disease. AEs that meet the above criteria but occur after the DLT evaluation period will not be defined as DLTs but will be reported as AEs/Serious Adverse Events (SAEs), as applicable, and will be reviewed across all cohorts during the study to help inform dose escalation decisions.

In case of suspicion of a DLT, the Investigator must inform the Medical Monitor/Sponsor immediately. The DLT will be confirmed by the Medical Monitor/Sponsor and a decision must be taken by the Sponsor regarding if an *ad hoc* SRC meeting is required.

Patients who discontinue therapy before completion of 2 cycles (DLT period) for other reasons than dose-limiting toxicity will be replaced. Patients who are tolerating PTX-35 will not have to discontinue study treatment prematurely due to the occurrence of DLTs in another patient in the same cohort, unless decided by the SRC.

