### **7.3.2 Days 2, 4, 7, and 10 of Cycle 1 and Cycle 2**

- Blood sample for pharmacokinetics at the following post-dose time points:  
Day 2 - 24hr ( $\pm 2$ hr), Day 4 – 72hr ( $\pm 2$ hr), Day 7 – 144hr ( $\pm 2$ hr) and Day 10 – 216hr ( $\pm 2$ hr)
- Blood sample for immunological effect (Day 7 only)
- Concomitant medications review
- Adverse event assessment

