### 9.1 Analysis Populations

Safety Evaluable Population: All patients who received at least 1 dose of PTX-35.

DLT Evaluable Population: All patients who receive at least 1 dose of PTX-35 and experience a DLT and/or complete the DLT evaluation period.

Efficacy Evaluable Population: All patients with pre-treatment measurable disease by RECIST 1.1, who received at least 1 dose of PTX-35 and who had at least one radiological assessment during treatment.

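### No hematology or chemistry is scheduled between the dose 2 visit and the end of the 4-week DLT window, and no such result is required before the SRC decides on escalation

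*Combined protocol and SAP*

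**What the plan says.** **Window and decision.** Section 6.1.3 defines the DLT window as the "4 week evaluation period following the initial administration of PTX-35", which covers Cycles 1 and 2. Under section 6.1.2 the SRC reviews a level "After all 3 patients in a dose level have received the second dose of PTX-35 and completed the DLT observation period". The same section names laboratory data as part of safety: "Safety will be assessed by frequency of treatment-emergent adverse events (TEAEs), evaluation of clinical laboratory parameters (hematology and biochemistry" and other measures follow in that sentence.

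**Who counts.** The DLT-evaluable population in section 9.1 is "All patients who receive at least 1 dose of PTX-35 and experience a DLT and/or complete the DLT evaluation period". It sets no laboratory condition. Section 8.1.2.7.1 has the SRC evaluate the data obtained at each level, including all adverse events, without a minimum laboratory data set.

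**Schedule.** Table 2 and sections 7.2 to 7.4 place hematology and chemistry at screening, on Day 1 of every cycle and at the 30-day visit. The visits on "Days 2, 4, 7, and 10 of Cycle 1 and Cycle 2" (section 7.3.2) have PK sampling, an immunology sample on Day 7, medication review and adverse event assessment, but no hematology or chemistry. Section 7.3.3 adds a cytokine sample 2 hours after the dose 2 infusion.

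**DLT criteria.** An event is a DLT if it "meets at least one of the criteria below". The list includes any hematological or non-hematological toxicity of Grade 3 or higher. A hepatic bullet has its own duration limit: "CTCAE G3 AST or ALT for" more than 7 consecutive days. The exclusion list removes other self-limited or medically controllable Grade 3 events, lymphopenia among the examples, but "such events are considered DLT if the abnormality leads to hospitalization or the abnormality persists for" more than 72 hours.

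**The concern.** The number of DLTs is the first primary endpoint and the sole input to the 3+3 rule. Several DLT criteria are laboratory grades, some with a duration attached. If no blood is tested between the dose 2 visit and the end of the window, a patient can be counted as DLT-free after two doses on laboratory evidence that essentially covers one dose.

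Symptomatic events should surface at the adverse event assessments on Days 2, 4, 7 and 10. A silent cytopenia or transaminase rise would not. The error runs one way: DLTs are under-counted and a level passes more easily, in a first-in-human trial with no earlier human safety data.

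**Working it through.** **1. The plan's own calendar.** Two cycles of 14 days give 2 × 14 = 28 days, which reproduces the stated 4 weeks. Dose 1 is on Day 1.

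- Cycle 2 Day 1: Day 15, or up to Day 17 with the +2-day window.
- Cycle 3 Day 1: Day 29 at the earliest; Day 33 if both +2-day windows are used.
- 30-day visit after dose 2: 15 + 30 − 3 = Day 42 to 17 + 30 + 3 = Day 50.

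After the dose 2 visit, the number of scheduled hematology or chemistry draws up to Day 28 is zero. The draw on Cycle 2 Day 1 is not labelled pre-dose, but even if taken after the infusion it is a same-day sample.

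**2. Duration criteria.** A single draw cannot show persistence. Two draws at least 14 days apart cannot show that a value stayed abnormal for more than 72 hours or for more than 7 consecutive days. Detected events are followed (8.1.2.1) and dosing is delayed (6.2), but neither section gives a repeat-test interval. Grade 4 AST/ALT and bilirubin of Grade 3 or higher need no duration, so one draw would suffice for those, if one were taken.

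**3. Detection (illustration).** Assume onset uniform from Day 1 to Day 29 and scheduled draws only. An episode of d days is detected if it covers a draw.

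- Draw on Day 15 only: d/28 for d up to 14, so 4/28 = 14% (4 days), 8/28 = 29% (8 days), and at most 14/28 = 50%. With the draw on Day 17 the ceiling is 16/28 = 57%.
- Draws on Days 15 and 29: 2d/28, so 8/28 = 29% (4 days), 16/28 = 57% (8 days), and 100% from 14 days on.
- Draws on Days 7, 15, 21 and 29: 16/28 = 57% (4 days) and 100% (8 days).

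**4. Effect on the 3+3 rule (illustration).** Let p be the true DLT rate, s the share of DLTs that are laboratory-only, and det the detection above. The observed rate is q = p[1 − s(1 − det)], and P(escalate) = (1 − q)³ + 3q(1 − q)⁵. Neither p nor s comes from the documents. Every 4- to 8-day silent episode is counted as a DLT, and SRC discretion is not modelled.

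With p = 0.33 and s = 0.25:

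| Draws | Episode | q | P(escalate) |
|---|---|---|---|
| All DLTs seen | any | 0.330 | 43.4% |
| Days 15 and 29 | 8 days | 0.295 | 50.5% |
| Days 15 and 29 | 4 days | 0.271 | 55.5% |
| Day 15 only | 8 days | 0.271 | 55.5% |
| Day 15 only | 4 days | 0.259 | 58.0% |
| Days 15 and 29 | 14 days or more | 0.330 | 43.4% |
| Days 7, 15, 21 and 29 | 8 days | 0.330 | 43.4% |
| Days 7, 15, 21 and 29 | 4 days | 0.295 | 50.5% |

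Example for row two: q = 0.33 × [1 − 0.25 × (1 − 0.571)] = 0.295, and 0.705³ + 3 × 0.295 × 0.705⁵ = 0.505 (unrounded q). With s = 0.10, the 4- to 8-day range is 46.2-48.1% when everyone has the Day 29 draw and 48.1-49.1% when no one does.

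**5. Grade 3 AST/ALT in section 6.1.3.**

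- More than 7 days: a DLT under both the general non-hematological bullet and the hepatic bullet.
- More than 72 hours, up to 7 days: a DLT under the general bullet, and still one under the 72-hour note if the event is first treated as controllable; not one under the hepatic bullet.
- 72 hours or less: depends on whether the exclusion for self-limited or controllable Grade 3 events reaches transaminases.

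Because one criterion is enough, the hepatic 7-day limit has no effect in the middle band.

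**The case against.** The plan has real safeguards. Patients without progression or unacceptable toxicity may go on to Cycle 3, where laboratory tests are drawn, and an abnormality seen then with onset in Cycle 2 can still count. First on-study imaging is at 8 weeks (±1 week), so no scheduled scan prompts stopping at Day 29. Patients who stop early for reasons other than toxicity are replaced (5.4.2). The first patient starts at least a week ahead of the others, so that patient's Cycle 3 draw will normally precede the SRC review. Later events inform escalation, and the SRC may ask for more patients. All of this stands and narrows the gap. None of it reveals a value that was never measured, and the Cycle 3 draw is not a condition for the decision.

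A reader might go further in four ways that the documents do not support.

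- That no safety laboratory sample at all follows dose 2. The cytokine sample does, and section 9.3 lists cytokines among the laboratory evaluations. It cannot grade cytopenias or liver tests.
- That an end-of-window draw improves detection for everyone. For a patient with Cycle 3 Day 1 on Day 29, it is the same draw.
- That 58% is the expected escalation probability. That figure needs every patient in the cohort to skip the Cycle 3 draw, and all silent episodes to last 4 days.
- That every Grade 3 AST/ALT rise of 7 days or less is plainly a DLT under the general bullet. For 72 hours or less, the exclusion list may remove it.

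**Conclusion.** The gap is real and follows from the calendar alone: no scheduled hematology or chemistry after the dose 2 visit within the DLT window, and no requirement for such a result before the SRC decides. The direction is under-counted DLTs and easier escalation. The size cannot be known, because the documents give neither the laboratory-only share of DLTs nor how long such events last. The illustrated effect runs from none (episodes of 14 days or more with a Day 29 draw) to about 15 percentage points (58.0 − 43.4 = 14.6), under assumed uniform onset, a 33% DLT rate and a 25% laboratory-only share. This should be fixed, though it does not undermine the design.

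The Grade 3 AST/ALT conflict is a separate matter and is wrong as written: for a rise lasting more than 72 hours and up to 7 days, two readers can score the same event differently.

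**What to change.** 1. In Table 2, 6.1.2 and 9.1, require an end-of-window hematology and chemistry result for every DLT-evaluable patient, available to the SRC before it decides. Cycle 3 Day 1 can serve when drawn on time. The gain lies with patients who do not start Cycle 3 and in the timing of the SRC review. Cost: about 10 mL of blood, and an added visit only for those patients.
2. In Table 2 and 7.3.2, add hematology and chemistry to a mid-cycle visit where blood is already drawn. Day 7 of Cycles 1 and 2 is the lighter option: two draws, about 20 mL. State the repeat-test interval after a detected abnormality, so that the 72-hour and 7-day durations can be determined. Cost: laboratory fees and occasional repeat tests. More brief Grade 3 values will be found, so more levels may expand from 3 to 6 patients.
3. Reconcile the general non-hematological bullet, the hepatic bullet and the exclusion list in 6.1.3 for Grade 3 AST/ALT. This review does not choose the rule. Cost: a text change in the same amendment, repeated in the synopsis.

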### 6.1.3 Dose-Limiting Toxicity

An event will be considered a DLT per NCI CTCAE version 5.0 criteria if it occurs within the DLT reporting period during Cycle 1 and Cycle 2 (i.e., 4 week evaluation period following the initial administration of PTX-35) and meets at least one of the criteria below:

- Hematological toxicities  $\geq$  Grade 3
- Non-hematological toxicities  $\geq$  Grade 3
- Cytokine release syndrome  $\geq$  Grade 3
- Infusion reaction  $\geq$  Grade 3
- Any  $\geq$  Grade 3 hepatic toxicity meeting Hy's Law criteria, or total bilirubin  $\geq 2.0 \times$  ULN to  $\leq 3.0 \times$  ULN for  $>7$  consecutive days,  $\geq$  CTCAE G3 total bilirubin, CTCAE G3 AST or ALT for  $>7$  consecutive days, or CTCAE G4 AST or ALT
- Any other treatment-emergent toxicity that is considered clinically significant and/or unacceptable, and that does not respond to supportive care and results in a disruption of the treatment schedule of more than 14 days.

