**Dose-Limiting Toxicity (DLT):**

An event will be considered a DLT per NCI CTCAE version 5.0 criteria if it occurs within the DLT reporting period and meets at least one of the criteria below:

- Hematological toxicities  $\geq$  Grade 3
- Non-hematological toxicities  $\geq$  Grade 3
- Cytokine release syndrome  $\geq$  Grade 3
- Infusion reaction  $\geq$  Grade 3
- Any  $\geq$  Grade 3 hepatic toxicity meeting Hy's Law criteria, or Total bilirubin  $\geq 2.0 \times$  ULN to  $\leq 3.0 \times$  ULN for  $>7$  consecutive days,  $\geq$  CTCAE G3 total bilirubin, CTCAE G3 AST or ALT for  $>7$  consecutive days, or CTCAE G4 AST or ALT
- Any other treatment-emergent toxicity that is considered clinically significant and/or unacceptable, and that does not respond to supportive care and results in a disruption of the treatment schedule of more than 14 days.

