## 5.0 SELECTION AND WITHDRAWAL OF PATIENTS

### 5.1 Inclusion Criteria

Patients **must** meet all of the following inclusion criteria before they will be allowed to participate in the trial:

1. Be willing and have the capacity to sign the written informed consent form.
2. Be male or female of at least 18 years of age at the time of signing informed consent.
3. Have a documented diagnosis of metastatic or advanced, unresectable solid tumor disease. Patient must have progressed or recurred following standard of care (SOC) therapies, or are ineligible for, or who refuse, other safe and effective SOC therapies, and whom the Investigator believes may benefit from experimental treatment with PTX-35.

4. Have an acceptable organ function, as defined below:
  - a. Albumin  $\geq$  2.5 g/dL
  - b. Total bilirubin  $< 3.0 \times$  upper limit of normal (ULN) unless patient has Gilbert's syndrome.
  - c. Alanine transaminase (ALT) and aspartate transaminase (AST)  $\leq 3.0 \times$  ULN, or  $\leq 5 \times$  ULN in the case of liver metastases.
  - d. Calculated or measured creatinine clearance  $> 35$  mL/minute per the Cockcroft-Gault formula.
  - e. Absolute neutrophil count  $\geq 1,500/\text{mm}^3$
  - f. Hemoglobin  $\geq 9$  g/dL.
  - g. Platelet count  $\geq 100,000/\text{mm}^3$
5. Have an Eastern Cooperative Oncology Group (ECOG) performance status of 0 to 2 ([APPENDIX I](#)).
6. Have life expectancy of at least three months.
7. Patients, both females and males, of childbearing/reproductive potential must agree to use adequate contraception, or continuous abstinence, while included in the trial and for six months after the last treatment with PTX-35.

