#### 8.1.2 Reporting of Adverse Events

##### 8.1.2.1 Adverse Events

An adverse event (AE) is any untoward medical occurrence in a patient or clinical investigation subject administered a pharmaceutical product that does not necessarily have a causal relationship with the treatment. An adverse event can be any unfavorable and unintended sign (including a laboratory finding), symptom or disease temporally associated with the use of an Investigational Product, whether or not related to the Investigational Product.

The AE reporting period starts on Cycle 1 Day 1 after the first dose of PTX-35. If an AE occurs before the first dose of study drug it will be captured as baseline and considered part of medical history unless it directly related to a study procedure (in which case it may be reported as an AE). At each evaluation, patients should be interviewed in a non-directed manner to elicit potential adverse reactions from the patient. The occurrence of an adverse event will be based on changes in the patient's physical examination, laboratory results, and/or signs and symptoms.

All adverse events (except Grade 1 and 2 laboratory abnormalities that do not require an intervention), regardless of causal relationship, are to be recorded in the case report form and source documentation. The Investigator must determine the intensity of any adverse events according to the NCI Common Terminology Criteria for Adverse Events (CTCAE) version 5.0 and their causal relationship. Those AEs not covered by these criteria will be graded as follows:

1. Mild: Discomfort noticed, but no disruption of normal daily activity. Prescription drug not ordinarily needed for relief of symptom but may be given because of personality of patient.
2. Moderate: Discomfort sufficient to reduce or affect normal daily activity. Patient is able to continue in study; treatment for symptom may be needed.
3. Severe: Incapacitating, severe discomfort with inability to work or to perform normal daily activity. Severity may cause cessation of treatment with test drug; treatment for symptom may be given and/or patient hospitalized.
4. Life-Threatening: Symptom(s) place the patient at immediate risk of death from the reaction as it occurred; it does not include a reaction that, had it occurred in a more serious form, might have caused death.
5. Fatal: Event caused the death of the patient.

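### The bilirubin DLT criterion (2.0 to 3.0 × ULN for more than 7 days) overlaps the entry range and has no baseline term, so a trivial post-dose rise can count as a DLT

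*Combined protocol and SAP*

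**What the plan says.** - **DLT criterion.** Section 6.1.3 lists, among criteria of which any one suffices, "total bilirubin $\geq 2.0 \times$ ULN to $\leq 3.0 \times$ ULN for $>7$ consecutive days". The synopsis has the same limb: "Total bilirubin $\geq 2.0 \times$ ULN to $\leq 3.0 \times$ ULN for $>7$ consecutive days". Neither refers to the value before dosing.
- **Entry.** Section 5.1, criterion 4b (repeated in the synopsis), requires total bilirubin below 3.0 × "upper limit of normal (ULN) unless patient has Gilbert's syndrome". No other limit replaces it in Gilbert's syndrome.
- **What counts as an event.** Section 8.1.2.1 treats findings before the first dose as medical history and adds: "The occurrence of an adverse event will be based on changes in the patient's physical examination, laboratory results, and/or signs and symptoms". It gives no minimum size of change.
- **Exclusions and attribution.** Section 6.1.3 excludes toxicities of Grade 2 or lower "unless considered non-acceptable". It also presumes relatedness: "A DLT will be considered related to PTX-35 treatment unless there is a clear, well-documented relation to intercurrent illness or primary malignant disease". The Medical Monitor/Sponsor confirms each suspected DLT.
- **Use of the count.** The number of DLTs is a primary endpoint (9.2.1). One DLT in three patients expands a level to at least six and two stop escalation (6.1.2). The MTD is defined by the same count (6.1.4).

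**The concern.** A DLT should mark harm that appears after dosing. Here the eligibility criteria deliberately admit patients whose bilirubin already lies where the DLT limb begins to count, and the limb does not ask how far the value has moved. A patient who enters at 2.3 × ULN and drifts to 2.5 × ULN for more than a week satisfies the wording, although such a change could be ordinary fluctuation of a chronic abnormality.

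With three patients per level, one such count commits the trial to at least three more patients and another four-week window. A second DLT at that level, real or not, ends escalation. The result would be an MTD set too low, not an overdose. The decision would also be made case by case, on a primary endpoint in an open-label trial, with no stated baseline criterion to guide it.

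**Working it through.** The plan gives no figure that depends on this limb, so there is none to reproduce. The check compares the thresholds, then traces the consequence.

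**1. Overlap.** The DLT band is 2.0 to 3.0 × ULN (6.1.3). The entry range is below 3.0 × ULN (5.1), and uncapped in Gilbert's. Apart from the single point 3.0, the band lies inside the ordinary entry range. In Gilbert's it lies wholly inside.

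**2. Size of rise that can count.**
- From 1.9 to 2.0 × ULN: 0.1/1.9 = 5.3%, enough to reach the band.
- From 1.9 to 2.1 × ULN: 2.1/1.9 = 1.11, a rise of 11%.
- From 2.3 to 2.5 × ULN: 2.5/2.3 = 1.09, a rise of 9%.

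Each meets the limb if it lasts more than 7 days.

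**3. Does other text set a minimum rise?** Section 8.1.2.1 requires a change but gives no size. Section 6.1.3 provides central confirmation without a baseline criterion. Attribution can be rebutted by intercurrent illness or the malignancy, but the text does not say whether Gilbert's or another chronic non-malignant cause qualifies. None of these supplies a minimum.

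**4. Can the scheduled draws show more than 7 days?** Chemistry is drawn within 7 days before C1D1 (7.2), at C1D1 or up to 3 days earlier (7.3.1), and at C2D1, which is Day 15 to 17 (7.3.3). None is listed for Days 2, 4, 7 and 10 (7.3.2). C3D1 is Day 29 at the earliest (7.3.4), at or beyond the end of the four-week window. So C2D1 is the only scheduled post-dose chemistry clearly inside the window, and duration has to come from unscheduled draws.

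**5. Consequence of one counted case.** Assume one of the first three patients is counted only through this limb, the other patients have true DLT rate t (not given in the documents), and an expanded level has exactly six patients.
- Counted: the level stops if any of the other five has a DLT, so P = 1 − (1 − t)^5.
- Not counted: P = t² + 2t(1 − t)[1 − (1 − t)³].

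| t | Counted | Not counted |
|---|---|---|
| 0 | 0 | 0 |
| 2% | 9.6% | 0.3% |
| 5% | 22.6% | 1.6% |
| 10% | 41.0% | 5.9% |

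At t = 0 the single case forces expansion but cannot stop the level. These figures are conditional on the case having occurred.

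**6. Scale if frequency is assumed.** Let a share q of patients be counted this way, with no true toxicity. The documents give no source for q.
- Per-level stop: P(at least 2 of 3) + P(1 of 3) × P(at least 1 of next 3). For q = 0.5%, 1% and 2% this is 0.03%, 0.1% and 0.5%.
- Over seven levels, 1 − (1 − p)^7, where p is the per-level stop probability: 0.2%, 0.8% and 3.2%.

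**7. Check of the proposed rule.** With a multiple of 1.5, the threshold is the larger of 2.0 and 1.5 × baseline, in ULN units. The multiple binds above a baseline of 2.0/1.5 = 1.33. At baseline 1.9 the threshold is 2.85, and at 2.3 it is 3.45, so the examples in step 2 no longer count. If the 3.0 ceiling were kept, the test could not be met above a baseline of 3.0/1.5 = 2.0. That is why the ceiling has to go.

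**The case against.** The strongest reply is that an absolute threshold with presumed relatedness is a deliberately cautious first-in-human choice, and that several filters already apply. An event requires change, the Medical Monitor/Sponsor confirms it centrally, a documented relation to the malignancy rebuts it, and the Safety Review Committee may choose an intermediate level or add patients (8.1.2.7.1). Documenting the duration needs unscheduled blood draws. The conditional stop probabilities would apply to any single DLT in a 3+3 design.

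All of this stands, and it keeps the point small. It does not close the gap, because no filter says how large a rise must be.

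A reader might infer more than the text supports:
- **That an unchanged in-band value is a DLT.** Section 8.1.2.1 makes the pre-dose value medical history and bases events on change.
- **That the C1D1 and C2D1 values together show more than 7 days.** The C1D1 value is pre-dose, so it cannot start an event in a window that follows the first dose. Two isolated values do not document consecutive days either.
- **That the exclusion of Grade 2 or lower voids the limb.** CTCAE cut-offs are not in the documents, and a specific limb with a duration can stand beside a general exclusion that allows for unacceptable events.
- **That the recording exemption, "except Grade 1 and 2 laboratory abnormalities that do not require an intervention", removes the case.** It governs what is recorded as an adverse event, not the DLT definition.
- **That Section 6.2 would impose long dose delays.** It generally allows restart at Grade 2 or lower. If the band is Grade 2 or lower, that condition is already met.

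**Conclusion.** The overlap is real, and the missing baseline term is a gap in the DLT definition. Followed as written, the limb can count a rise of about 10% from an abnormal baseline toward a primary endpoint that drives escalation and the MTD. The case is probably rare and the error is conservative, so this is an inexpensive correction, not a threat to patient safety or to the trial's validity.

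The frequency cannot be estimated, because the documents do not say how many patients will enter near or above 2.0 × ULN. The percentages in the table assume that the case has already occurred and assume t; the values of q are illustrations only. The conclusion itself rests on the wording of Sections 5.1, 6.1.3 and 8.1.2.1.

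It would be tempting to apply the same baseline condition to Grade 3 bilirubin. The documents do not support this: they do not reproduce CTCAE v5.0, so whether grading already allows for an abnormal baseline cannot be checked. Making a Grade 3 rise wait more than 7 days would weaken hepatic protection in a first-in-human trial.

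**What to change.** In Section 6.1.3 and the synopsis:
1. When pre-dose bilirubin is at or below ULN, keep the 2.0 to 3.0 × ULN limb as written.
2. When pre-dose bilirubin is above ULN, including in Gilbert's syndrome, count this limb only if bilirubin is at least 2.0 × ULN and at least a pre-set multiple of the patient's own pre-dose baseline for more than 7 consecutive days after dosing. A multiple of 1.5 is an example for the sponsor to confirm. Apply no 3.0 × ULN ceiling to this test.
3. Leave unchanged the Grade 3 bilirubin limb (with no waiting period), the general bullet "Non-hematological toxicities $\geq$ Grade 3", the Hy's Law and AST/ALT limbs, and eligibility.

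The cost is a few sentences. Baseline chemistry is already drawn within 7 days before C1D1 and at C1D1, so no new scheduled test is needed; documenting the duration will depend on unscheduled draws, as it does now. The downside is that a true but small worsening from an abnormal baseline would not count as a DLT. It would still be visible to the Safety Review Committee, which evaluates the data from each dose level, laboratory parameters included.
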